8.2.4 Pneumonitis

Pneumonitis has been observed in subjects receiving trametinib monotherapy and trametinib in combination with dabrafenib. To reduce the risk of pneumonitis, subjects will be monitored closely for symptoms and evaluated with imaging and functional tests. Dose modification and supportive care guidelines for pneumonitis are described in Table 22.

Table 22 Guidelines for Management and Dose Modification for Pneumonitis

CTCAE Grade	Adverse Event Management	Action and Dose Modification
Grade 1	
 • CT scan (high-resolution with lung windows) recommended • Clinical evaluation and laboratory work-up for infection • Monitoring of oxygenation via pulse- oximetry recommended • Consultation of pulmonologist recommended 	
 • Continue trametinib at current dose
Grade 2	
 • CT scan (high-resolution with lung windows) • Clinical evaluation and laboratory work-up for infection 	
 • Interrupt trametinib until recovery to Grade \leq1 • Restart with trametinib reduced by one dose level
Grade 3	
 • Consult pulmonologist • Pulmonary function tests – if < normal, repeat every 8 weeks until \geq normal • Bronchoscopy with biopsy and/or BAL recommended • Symptomatic therapy including corticosteroids if clinically indicated 	
 • Consider use of corticosteroids prior to and during restart • Escalation to previous dose level is possible after 4 weeks and consultation with the Medical Lead • If no recovery to Grade \leq1 within 4 weeks, permanently discontinue trametinib

CTCAE Grade	Adverse Event Management	Action and Dose Modification
Grade 3 cont...	
 CT scan (high-resolution with lung windows) Clinical evaluation and laboratory work-up for infection Consult pulmonologist Pulmonary function tests-if < normal, repeat every 8 weeks until ≥ normal Bronchoscopy with biopsy and/or BAL if possible Symptomatic therapy including corticosteroids as clinically indicated 	
 Interrupt trametinib until recovery to Grade ≤1 After consultation with the Medical Lead, trametinib may be restarted reduced by one dose level Consider use of corticosteroids prior to and during restart If no recovery to Grade ≤1 within 4 weeks, permanently discontinue trametinib
Grade 4	
 Same as Grade 3 	
 Permanently discontinue trametinib

Abbreviations: BAL, bronchioalveolar lavage; CT, computed tomography

8.2.5 Diarrhea

Episodes of diarrhea have occurred in subjects receiving dabrafenib in combination with trametinib and /or trametinib monotherapy. Other frequent causes for diarrhea, including concomitant medications (e.g., stool softeners, laxatives, antacids, etc.), infections by *C. difficile* or other pathogens, partial bowel obstruction, should be clinically excluded.

Guidelines regarding management and dose reduction for diarrhea considered to be related to dabrafenib and/or trametinib by the investigator are provided in Table 23.

Table 23 Management and Dose Modification Guidelines for Diarrhea

Grade	Management	Action and Dose Modification
Uncomplicated Diarrhea¹ Grade 1 or 2	
 Diet: stop all lactose-containing products, eat small meal portions; recommend bland diet to avoid fatty and greasy foods, raw fruits and vegetables, alcohol, dairy products, and citrus fruits Hydration: 8 to 10 large glasses of clear liquids per day (e.g., Gatorade or broth) Loperamide³: initially 4 mg, followed by 2 mg every 4 hrs or after every unformed stool; maximum 16 mg/day. Continue until diarrhea free for 12 hrs Diarrhea > 24h: loperamide 2 mg every 2 hrs; maximum 16 mg/day. Consider adding oral antibiotics Diarrhea > 48h: loperamide 2 mg every 2 hrs; maximum 16 mg/day. Add budesonide or other second-line therapies (otretotide, or tincture of opium) and oral antibiotics 	
 Continue treatment with trametinib and dabrafenib If diarrhea is Grade 2 for >48 hrs, interrupt treatment with trametinib and dabrafenib until diarrhea resolves to ≤Grade 1 Restart treatment with trametinib and dabrafenib at the same dose levels
Uncomplicated Diarrhea¹ Grade 3 or 4	
 Clinical evaluation mandatory Loperamide³: initially 4 mg, followed by 2 mg every 4 hrs or after every unformed stool; maximum 	
 Interrupt treatment with trametinib and dabrafenib

Grade	Management	Action and Dose Modification
Any Complicated Diarrhea²	
16 mg/day. Continue until diarrhea-free for 12 hrs
 
 • Oral antibiotics and second-line therapies if clinically indicated • Hydration: IV fluids if clinically indicated • Antibiotics (oral or IV) if clinically indicated • Intervention should be continued until the subject is diarrhea-free for ≥24 hrs • Intervention may require hospitalization for subjects at risk of life-threatening complications 	
until diarrhea resolves to ≤Grade 1
 
 • Restart treatment with trametinib and dabrafenib each reduced by one dose level⁴ • If 3 dose reductions of trametinib and dabrafenib are clinically indicated, permanently discontinue treatment with trametinib and dabrafenib.

Abbreviation: hrs, hours; IV, intravenous; PS, performance status

1. Uncomplicated diarrhea defined by *absence of* symptoms: cramping, nausea/vomiting ≥Grade 2, decreased PS, pyrexia, sepsis, neutropenia ≥Grade 3, frank bleeding, and/or dehydration requiring IV fluid substitution.
2. Complicated diarrhea defined by *presence of* symptoms: cramping, nausea/vomiting ≥Grade 2, decreased PS, pyrexia, sepsis, neutropenia ≥Grade 3, frank bleeding, and/or dehydration requiring IV fluid substitution.
3. Loperamide should be made available prior to start of study treatment so loperamide administration can begin at the first signs of diarrhea.
4. Escalation of trametinib and dabrafenib to previous dose level is allowed after consultation with the Medical Lead and in the absence of another episode of complicated or severe diarrhea in the 4 weeks subsequent to dose reduction.

8.2.6 Renal Insufficiency

Cases of renal insufficiency have occurred in subjects receiving dabrafenib and the combination of dabrafenib and trametinib. Prior to start of study treatment, concomitant medications should be reviewed for the potential risk of inducing nephrotoxicity and concomitant medications should be modified if clinically possible.

Guidelines regarding management and dose reduction for renal insufficiency considered to be related to study treatment by the investigator are provided in Table 24.

Table 24 Management and Dose Modification Guidelines for Renal Insufficiency

Serum Creatinine Level	Adverse Event Management	Action and Dose Modification
Serum creatinine increase >0.2 mg/dL (18 umol/L) but ≤0.5 mg/dL	
 • Recheck serum creatinine within 1 week • Serum creatinine increase >1 week: contact the Medical Lead. If elevation 	
 • Continue study treatment at the same dose level

(44 umol/L) above baseline	
persists beyond 4 weeks, recommend evaluation (consider renal biopsy) for etiology; consider nephrology consultation.
 
 • If pyrexia is present, treat pyrexia as per guidelines¹ 	

Serum creatinine increase >0.5 mg/dL (44 umol/L) above baseline or serum creatinine >2 mg/dL (>177 umol/L)
	
 • Monitor serum creatinine ≥ 2 times per week • Hospitalization may be necessary if serum creatinine cannot be monitored frequently • If pyrexia is present, treat pyrexia per guidelines¹ • Consult nephrologist if clinically indicated • Perform renal biopsy if clinically indicated, for example: 
 • Renal insufficiency persists despite volume repletion • Subject has new rash or signs of hypersensitivity (such as elevated eosinophil count) 	
 • Interrupt study treatment until serum creatinine recovers to baseline • Restart with study treatment²

Abbreviations: NSAIDs, non-steroidal anti-inflammatory drugs

1. NSAIDs can induce renal insufficiency, especially in subjects with dehydration; encourage oral fluids or consider intravenous fluids as clinically indicated. See guidelines for pyrexia in Section 8.2.3.
2. Investigator may restart at either the same or a reduced dose level. Escalation of study treatment to previous dose level is allowed if another episode of renal insufficiency does not occur after 4 weeks of dose reduction. Consultation with the Medical Lead is required before restarting study treatment if there is evidence of thrombotic microangiopathy.

8.2.7 Visual Changes

Episodes of visual changes have been observed in subjects receiving trametinib, dabrafenib and combination therapy. An ophthalmologist should be consulted if changes in vision develop. However, if the visual changes are clearly unrelated to study treatment (e.g., allergic conjunctivitis), then monitor closely as it may be reasonable to defer ophthalmic examination. Treatment with dabrafenib has been associated with the development of uveitis, including iritis. Monitor subjects for visual signs and symptoms (such as, change in vision, photophobia and eye pain) during therapy.

Special attention should be given to retinal findings (e.g., RPED) or retinovascular abnormalities (i.e., branch or central RVO). For events of visual changes (regardless of severity) for which an ophthalmic examination is conducted, a blood sample for PK analysis must be drawn as close as possible to the time of the event.

Guidelines regarding management and dose reduction for visual changes considered to be related to trametinib treatment are provided in Table 25.

For events of uveitis and related toxicities (e.g. iritis, iridocyclitis), no dose modifications are required as long as effective local therapies can control ocular inflammation. If uveitis does not respond to local ocular therapy, withhold dabrafenib until resolution

of ocular inflammation and then restart dabrafenib reduced by one dose level. No dose modification of trametinib is required when taken in combination with dabrafenib.

Table 25 Management and Dose Modification Guidelines for Visual Changes and/or Ophthalmic Examination Findings

CTCAE Grade ¹	Adverse Event Management	Action and Dose Modification
Grade 1 ²	
 Consult ophthalmologist within 7 days of onset 	
 If dilated fundus examination cannot be performed within 7 days of onset, interrupt treatment with trametinib until RPED and RVO can be excluded by retina specialist/ophthalmologist. Dabrafenib may be continued. If RPED and RVO excluded, continue (or restart) treatment with trametinib at same dose level If RPED suspected or diagnosed: see table below; report as SAE if diagnosed. If RVO diagnosed: Permanently discontinue trametinib and report as SAE.
Grade 2 and Grade 3	
 Consult ophthalmologist immediately Interrupt treatment with trametinib. If subject is receiving trametinib/dabrafenib combination therapy dabrafenib may be continued 	
 If RPED and RVO excluded, restart trametinib at same dose level If RPED diagnosed, see RPED dose modification table (Table 26); report as SAE. If RVO diagnosed, permanently discontinue trametinib and report as SAE
Grade 4	
 Consult ophthalmologist immediately Interrupt treatment with trametinib. If subject is receiving trametinib/dabrafenib combination therapy dabrafenib may be continued 	
 If RPED and RVO excluded, may consider restarting trametinib at same or reduced dose after discussion with Medical Lead If RVO or RPED diagnosed, permanently discontinue trametinib and report as SAE.

Abbreviations: CTCAE, Common Terminology Criteria for Adverse Events; RPED, retinal pigment epithelial detachment; RVO, retinal vein occlusion; SAE, serious adverse event

- Refers to CTCAE Version 4.0 'Eye disorders – Other, specify'
- If visual changes are clearly unrelated to study treatment (e.g., allergic conjunctivitis), monitor closely but ophthalmic examination is not required.

Table 26 Recommended Dose Modifications for Trametinib for RPED

CTCAE Grade ¹	Action and Dose Modification
Grade 1 RPED (Asymptomatic; clinical or diagnostic observations only)	
 Continue treatment with dabrafenib + trametinib with retinal evaluation monthly until resolution. If RPED worsens follow instructions below and withhold trametinib for up to 3 weeks
Grade 2 or 3 RPED (Symptomatic with mild to moderate decrease in visual acuity; limiting instrumental ADL)	
 Interrupt trametinib for up to 3 weeks; continue treatment with dabrafenib Retinal evaluation monthly If improved to ≤ Grade 1 within 3 weeks, restart trametinib at lower dose (reduced by 0.5 mg) or discontinue in subjects taking trametinib 1 mg once daily

CTCAE Grade ¹	Action and Dose Modification
	

• Grade 2-3 RPED that does not improve to at least Grade 1 within 3 weeks, permanently discontinue trametinib.

Abbreviations: ADL, activities of daily living; CTCAE, Common Terminology Criteria for Adverse Events; RPED, retinal pigment epithelial detachment

1. Refers to retinopathy in CTCAE v4.0

9 LIFESTYLE AND/OR DIETARY RESTRICTIONS

9.1 Contraception Requirements

9.1.1 Female Subjects

Women of child-bearing potential, defined as all women physiologically capable of becoming pregnant, must use highly effective methods of contraception during dosing and for 16 weeks after stopping treatment.

Highly effective contraception methods include:

- a. Total abstinence (when this is in line with the preferred and usual lifestyle of the subject). Periodic abstinence (e.g., calendar, ovulation, symptothermal, post-ovulation methods) and withdrawal are not acceptable methods of contraception.
- b. Female sterilization (have had surgical bilateral oophorectomy with or without hysterectomy), total hysterectomy, or tubal ligation at least six weeks before taking study treatment. In case of oophorectomy alone, only when the reproductive status of the woman has been confirmed by follow up hormone level assessment.
- c. Sterilization (at least 6 months prior to screening) for male partners. The vasectomized male partner should be the sole partner for that subject.
- d. Placement of a hormonal or non-hormonal intrauterine device (IUD) or intrauterine system (IUS) with a documented failure rate of less than 1% per year.

Notes:

- a. Double-barrier contraception: condom and occlusive cap (diaphragm or cervical/vault caps) with a vaginal spermicidal agent (foam/gel/cream/suppository) are not considered highly effective methods of contraception.
- b. Hormonal based methods (e.g. oral contraceptives) are not considered as highly effective methods of contraception due to potential drug-drug interactions with dabrafenib and/or trametinib (see Section [10.2](#)).
- c. Women are considered post-menopausal and not of child bearing potential if they have had 12 months of natural (spontaneous) amenorrhea with an appropriate clinical profile (i.e. age appropriate, history of vasomotor symptoms) or have had surgical bilateral oophorectomy (with or without hysterectomy), total hysterectomy, or tubal ligation at least six weeks ago. In the case of oophorectomy alone, only when the reproductive status of the woman has been confirmed by follow up hormone level assessment is she considered not of child bearing potential.

All menstruating female subjects (as required per local requirements and/or regulations) must have a negative serum pregnancy test within 7 days prior to the first dose of study treatment(s), preferably as close to the first dose as possible. Subjects must have used highly

effective contraception since the pregnancy test and agree to use adequate contraception during the study and for 16 weeks following discontinuation of trametinib when taken in combination with dabrafenib, or for 2 weeks following discontinuation of dabrafenib monotherapy.

These allowed methods of contraception are only effective when used consistently, correctly and in accordance with the product label. The investigator is responsible for ensuring subjects understand how to properly use these methods of contraception.

If a subject becomes pregnant during the treatment period of the study, the study treatments should be stopped immediately.

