Fertility: There is no information on the effect of dabrafenib or trametinib on human fertility. Animal studies with dabrafenib monotherapy or in combination with trametinib have shown reproductive toxicity which may impair fertility in humans. In dogs, rats and mice given dabrafenib and in dogs given dabrafenib in combination with trametinib, male reproductive effects, including testicular degeneration/depletion with secondary epididymal oligospermia, have occurred without clear evidence of reversibility. Male subjects should be informed of the potential risk for impaired spermatogenesis, which may be irreversible. Trametinib may impair fertility in humans.

Pregnancy: No adequate and well-controlled studies of dabrafenib or trametinib in pregnant women have been conducted. Animal studies with trametinib and dabrafenib have shown embryo fetal developmental toxicities, including teratogenic effects. Dabrafenib or trametinib should not be administered to pregnant women or nursing mothers. Women of childbearing potential should use effective methods of contraception during therapy and for 16 weeks following discontinuation of trametinib when taken in combination with dabrafenib, or for 2 weeks following discontinuation of dabrafenib monotherapy. Dabrafenib may decrease the efficacy of oral hormonal contraceptives; therefore, an alternative method of contraception must be used. (see [Section 9.1.1](#) for acceptable methods of contraception.) If dabrafenib or trametinib is used during pregnancy, or if the subject becomes pregnant while taking dabrafenib or trametinib, the subject should be informed of the potential hazard to the fetus.

Lactation: It is not known whether dabrafenib or trametinib is excreted in human milk. Because many medicinal products are excreted in human milk, a risk to the nursing infant cannot be excluded. A decision should be made whether to discontinue nursing or to discontinue dabrafenib and/or trametinib, taking into account the importance of study treatment to the mother.

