Subjects will have radiologic tests to identify target lesions and to assess disease status per protocol-defined response assessment criteria. Subjects will be evaluated following the first dose of study treatment according to the assessment schedule (see Time and Events Table, Section 7.1). Assessments may be performed more frequently if medically necessary. A treatment cycle is 28 days. Subjects will be assessed for AEs, study treatment compliance, and use of concomitant medications.

Subjects will receive dabrafenib 150 mg BID orally plus trametinib 2 mg once daily orally on a continuous dosing schedule. Subjects will undergo disease assessment of response after receiving at least 8 weeks of treatment. Dose adjustments will be made as needed based on toxicity. Subjects will continue treatment until an unacceptable toxicity, disease progression, or death occurs. Subjects who continue on treatment will undergo disease assessment according to the applicable response assessment criteria for the specific histology (i.e., for solid tumors, radiologic assessment every 8 weeks following initial response assessment). Subjects who experience disease progression will discontinue study treatments and be withdrawn from the study, unless the investigator, with approval of the Medical Lead, indicates that the subject may receive clinical benefit from continued study treatment. Once a subject discontinues treatment and/or is withdrawn from the study, a post-treatment follow-up visit will be conducted within 28 days (+7 days) after the last dose of study treatment(s) with extended follow-up visits conducted every 4 weeks (± 7 days) for the first 6 months and then every 3 months (± 14 days) thereafter.

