4.1 Discussion of Design

The design of this Phase II study allows for the simultaneous evaluation of clinical activity and early signals of efficacy in each of the histologies under study. In addition, the safety of dabrafenib in combination with trametinib will be evaluated to support the use of the combination treatment in subjects with selected rare tumor types. Study treatment will begin on Study Day 1 and will continue until protocol-defined treatment withdrawal criteria are met (Section 16). While on study treatment, subjects will be closely monitored for safety. Procedures to minimize or monitor potential risks, dose modification guidance, and supportive care recommendations are provided in Section 8.1.

In the event one of the combination agents is discontinued, subjects may still receive the remaining agent (either dabrafenib or trametinib) as monotherapy provided the investigator concludes that continued therapy will be in the best interest of the subject and will result in potential clinical benefit. Once subjects are permanently withdrawn from all study treatments, a post-treatment follow-up assessment should be completed within approximately 28 days from the last dose of study treatment.

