5.4.1 Inclusion Criteria

Subjects must meet all of the following inclusion criteria in order to be considered eligible for this study:

1. Signed, written informed consent
2. Sex: male or female
3. Age: ≥ 18 years of age at the time of providing informed consent
4. Eastern Cooperative Oncology Group (ECOG) performance status: 0, 1 or 2 ([Appendix 1](#)).
5. Must have advanced disease and no standard treatment options as determined by locally/regionally available standards of care and treating physician's discretion.
6. Must have a BRAF V600E mutation-positive tumor as confirmed by an approved local laboratory or a sponsor designated central reference laboratory.
7. **NOTE:** All subjects must provide an archived or fresh tumor sample (for solid tumors) or a fresh BM aspirate and peripheral blood sample (for HCL and MM) for confirmation testing of the BRAF V600E mutation by a sponsor designated central reference laboratory using a sponsor designated assay. See Section 7.3.1 for additional details.
8. ATC, BTC, GIST, NSGCT/NGGCT, and ASI ONLY: Must have at least one measurable lesion per RECIST 1.1 outside of a prior radiation field or within the field with evidence of progression.
9. Able to swallow and retain orally administered medication.
10. Female Subjects of Childbearing Potential: Subjects must have a negative serum pregnancy test within 7 days prior to the first dose of study treatment and agrees to use highly effective contraception, as defined in Section 9.1, from 7 days prior to enrollment, throughout the treatment period and for 16 weeks following discontinuation of trametinib when taken in combination with dabrafenib, or for 2 weeks following discontinuation of dabrafenib monotherapy.
11. Has adequate baseline organ function as outlined in Table 3

Table 3 Adequate Baseline Organ Function

SYSTEM Adequate Baseline Organ Function	TEST	Histology	LABORATORY VALUES ¹	
Hematologic	ANC ³	ATC, BTC, GIST, WHO Grade 1-4 Glioma, NSGCT/NGGCT, ASI	$\geq 1.2 \times 10^9/L$	
		MM	$\geq 1 \times 10^9/L$	
	Hemoglobin ³	ATC, BTC, GIST, WHO Grade 1-4 Glioma, NSGCT/NGGCT, ASI	≥ 9 g/dL	
		Platelets ³	ATC, BTC, GIST, NSGCT/NGGCT, ASI	$\geq 75 \times 10^9/L$
			MM	$\geq 50 \times 10^9/L$
	WHO Grade 1-4 Glioma	$\geq 100 \times 10^9/L$		
PT, PTT, INR ²	ATC, BTC, GIST, WHO Grade 1-4 Glioma, NSGCT/NGGCT, ASI, HCL, MM	≤ 1.5 times ULN		
Hepatic	Albumin	ATC, BTC, GIST, WHO Grade 1-4 Glioma, NSGCT/NGGCT, ASI, HCL, MM	≥ 2.5 g/dL	
		ATC	≤ 1.5 times ULN	

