7.4.10 Pregnancy Testing and Reporting

7.4.10.1 Pregnancy Testing

The need for a screening pregnancy test depends on whether a female subject is of childbearing or non-childbearing potential.

A female of non-childbearing potential (i.e., physiologically incapable of becoming pregnant) is defined as any female who has had a hysterectomy, bilateral oophorectomy (ovariectomy) or bilateral tubal ligation, or is post-menopausal defined as 1 year without menses with an appropriate clinical profile, e.g., age appropriate, >45 years in the absence of hormone replacement therapy (HRT). In questionable cases, the subject must have a follicle stimulating hormone (FSH) value >40 mIU/mL and an estradiol value <40 pg/mL (<140 pmol/L).

A female of child-bearing potential is defined as any female who does not meet the criteria of non-childbearing potential as described in the previous paragraph.

If a female subject is of childbearing potential, she must have a serum β -HCG pregnancy test performed within 7 days prior to the first dose of study treatment. Subjects with a positive pregnancy test result must be excluded from the study. Subjects with a negative pregnancy test result must agree to use a highly effective contraception method (see Section 9.1) during the study and for 16 weeks following discontinuation of trametinib when taken in combination with dabrafenib, or for 2 weeks following discontinuation of dabrafenib monotherapy.

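### Section 9.1.1 gives conflicting post-treatment contraception periods for a woman who stops trametinib first and continues on dabrafenib alone

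*Protocol*

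**What the plan says.** The opening sentence of Protocol Section 9.1.1 says that women of child-bearing potential "must use highly effective methods of contraception during dosing and for 16 weeks after stopping treatment". It makes no distinction by drug or by the order in which the drugs are stopped.

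After the list of accepted methods, the same section states the period again, in two limbs: "16 weeks following discontinuation of trametinib when taken in combination with dabrafenib, or for 2 weeks following discontinuation of dabrafenib monotherapy". The two-limb wording recurs in three other places:

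- Section 1.4, under Pregnancy: "for 16 weeks following discontinuation of trametinib when taken in combination with dabrafenib", followed by the 2-week limb.
- Section 5.4.1, criterion 10: the same 16-week limb, or "for 2 weeks following discontinuation of dabrafenib monotherapy".
- Section 7.4.10.1: "during the study and for 16 weeks following discontinuation of trametinib when taken in combination with dabrafenib", followed by the 2-week limb.

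Two design features decide who can fall under the 2-week limb. Section 4 assigns the combination to everyone: "Subjects will receive dabrafenib 150 mg BID orally plus trametinib 2 mg once daily orally on a continuous dosing schedule". Section 4.1 provides that if one agent is discontinued, "subjects may still receive the remaining agent (either dabrafenib or trametinib) as monotherapy". Section 8.1 (Dose reduction) gives one route, since trametinib is stopped and dabrafenib may continue if trametinib would have to go below its lowest dose level. Tables 25 and 26 in Section 8.2.7 give others, with permanent discontinuation of trametinib for certain retinal events.

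**The concern.** Nobody in this study starts on dabrafenib alone. A woman on dabrafenib monotherapy has therefore ordinarily taken trametinib in combination first, and both limbs of the later paragraph describe her. They are joined by *or*, and nothing says whether the later date applies or whether the second limb displaces the first. The opening sentence gives her a third answer.

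Section 1.4 reports embryo-fetal toxicity in animals, including teratogenic effects, for both drugs. Section 9.1.1 makes the investigator responsible for seeing that subjects understand how to use the permitted methods. Two sites could each follow the text faithfully and give the same woman different end dates.

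The rule for men in Section 9.1.2 shows that the wording can be settled: it counts from the last dose, once both drugs are permanently discontinued. The women's rule has no such statement for drugs stopped at different times. The comparison concerns the form of the rule only, not the length of the period.

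**Working it through.** The protocol has no calculated figure to reproduce. The check is date arithmetic on the stated periods.

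**Inputs**

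- Opening rule of 9.1.1: 16 weeks after stopping treatment, taken here as the last dose of either drug.
- Later rule of 9.1.1 (also in 1.4, 5.4.1 and 7.4.10.1): 16 weeks from trametinib, or 2 weeks from dabrafenib monotherapy.
- d: weeks on dabrafenib alone, counted from the last trametinib dose. The documents give no value, so a range is shown as an assumption.

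**Formulas**, in weeks from the last trametinib dose:

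- Opening rule: d + 16.
- Later rule, both limbs apply: max(16, d + 2).
- Later rule, 2-week limb replaces the trametinib limb: d + 2.
- Opening rule minus both-limbs reading: (d + 16) − max(16, d + 2) = min(d, 14).
- Opening rule minus replacement reading: (d + 16) − (d + 2) = 14 for every d.
- Shortfall against 16 weeks from trametinib, replacement reading: max(0, 14 − d).

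**Results**

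| d | Opening rule | Both limbs | 2-week limb alone | Opening minus both limbs | Shortfall, 2-week limb alone |
|---|---|---|---|---|---|
| 1 | 17 | 16 | 3 | 1 | 13 |
| 4 | 20 | 16 | 6 | 4 | 10 |
| 8 | 24 | 16 | 10 | 8 | 6 |
| 12 | 28 | 16 | 14 | 12 | 2 |
| 14 | 30 | 16 | 16 | 14 | 0 |

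At d = 4, for example, the three readings end at weeks 20, 16 and 6. The both-limbs reading never ends before week 16. The opening rule ends later than that for any d above zero.

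**The other stopping sequences**

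- Both drugs stopped together (d = 0, no monotherapy): the opening rule and the trametinib limb both give 16 weeks, so there is no conflict.
- Dabrafenib stopped first, trametinib continued alone: read literally, the later rule names only trametinib taken in combination and dabrafenib monotherapy. This woman is covered by the opening rule and by no limb written for her case.

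**The case against.** A reader might infer that the protocol lets a woman who drops trametinib first stop contraception inside the trametinib risk period. The documents do not support that. Three things would all have to be true: the unqualified opening sentence of 9.1.1 is set aside; the *or* is read as letting the 2-week limb cancel a trametinib period already triggered; and dabrafenib monotherapy lasted under 14 weeks. Nothing says that the second limb cancels the first, and the first limb runs from an event that this woman has had. Read cumulatively, the later paragraph never releases her before week 16.

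A reader might also infer that a woman finishing on trametinib alone has no stated period, or that the later paragraph's shift from highly effective to adequate contraception permits weaker methods. Neither holds. The opening sentence covers the first case. For the second, Sections 5.4.1 and 7.4.10.1 require highly effective contraception through the post-treatment period and refer to Section 9.1, and 9.1.1 then refers back to its own list of allowed methods. The change of term, like the plain use of effective in Section 1.4, is loose wording and not a second tier.

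The practical reach is unknown. Enrollment ended on 29-Jun-2018, so criterion 10 no longer governs entry. The Amendment 11 rationale reports 55 subjects on treatment on 06-Apr-2020, without saying how many were women of child-bearing potential or had dropped trametinib alone. The consent pages and the study procedures manual were not available, so site counselling may be clearer than the protocol.

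These points limit the finding to sequential discontinuation and to a risk created by wording. They do not remove it, because the conflict survives the most favorable reading.

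**Conclusion.** This is an internal inconsistency in the current text. For a woman who stops trametinib and continues dabrafenib, the opening sentence and the later paragraph of 9.1.1 give different end dates for any d above zero. The difference is min(d, 14) weeks if both limbs apply and 14 weeks if the 2-week limb stands alone. An end date within 16 weeks of the last trametinib dose arises only on the second reading and only with d under 14.

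The result rests on two assumptions: that stopping treatment in the opening sentence means stopping the last study drug, and that d lies in a range which the documents do not give. No endpoint, analysis or sample-size figure is affected. The text should still be corrected, because it governs counselling on a fetal-exposure risk that the protocol itself describes. No view is taken here on which period is right.

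**What to change.** Reconcile both statements in Section 9.1.1 with Sections 1.4, 5.4.1 and 7.4.10.1. For each sequence (both drugs stopped together, trametinib stopped first, dabrafenib stopped first), state one period and the event from which it is counted. Where two limbs could apply to the same woman, say which governs. Use one term for the level of contraception throughout, and align the consent form. The choice of period is the sponsor's.

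The cost is wording in an amendment and the consent form, with the ethics review that these require. No data collection or analysis changes.
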